**6. SPECIFIC AIMS**

*Primary Objective*

The primary purpose of this study is to assess the efficacy of vaginal estrogen versus placebo at 6 months on the prevention of urinary tract infections (UTI) in postmenopausal women with history of recurrent UTI.

*Secondary Objectives*

- [1] a] To assess overall rates of UTI over 6 months in postmenopausal women with history of recurrent UTI receiving vaginal estrogen (ring or cream).
- b] To compare rates of UTI between 6 and 12 months of those subjects initially randomized to placebo.
- [2] To assess the impact of treatment of recurrent UTI with vaginal estrogen on quality of life at 6 and 12 months in postmenopausal women with history of recurrent UTI.
- [3] To assess compliance with vaginal estrogen (ring or cream) treatment at 12 months in postmenopausal women with history of recurrent UTI.
- [4] To assess efficacy of vaginal estrogen at 12 months in those compliant with treatment.

*Primary Hypothesis*

Vaginal estrogen (ring and cream) will be superior to placebo in the prevention of UTI at 6 months of treatment in postmenopausal women with a history of recurrent UTI.

*Secondary Hypotheses*

- [1] a] Overall rates of UTI in the first 6 month period in those women receiving vaginal estrogen will be

lower compared to those receiving placebo.

b) Rates of UTI will decrease between 6 and 12 months for those initially on placebo and subsequently using estrogen.

[2] Vaginal estrogen will result in improved QOL in postmenopausal women with history of recurrent UTI.

a) compared to placebo at 6 months.

b) compared to baseline at 12 months.

[3] Adherence with vaginal ring will be superior to cream.

[4] At 6 and 12 months, vaginal estrogen will be effective at preventing UTI in those adherent to therapy.

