The primary outcome is occurrence of one or more symptomatic UTIs within 6 months of treatment. Subjects will perform a clean catch for a urine culture when they have symptoms of a UTI using the CDC definition of symptoms, as above. If the subject cannot perform a clean catch themselves, a provider may obtain a catheterized specimen as clinically indicated, in which case the threshold for bacterial count will decrease to  $10^3$  microorganisms per mL. Secondary outcomes include assessing rate of UTI over the course of the year in those women who received placebo and then vaginal estrogen, as well as comparing the rates of UTI in the placebo and vaginal estrogen group. Quality of life (QOL) questionnaires will be administered at baseline, at the end of randomization and at drop out or 12 months. There are no validated questionnaires that assess UTI specifically, therefore we have chosen questionnaires which relate to general QOL, as well as those which include symptoms similar to that of UTI. In addition, we know that vaginal estrogen can treat dyspareunia, so we will capture sexual function. We will be using the SF 12, as well as the overactive bladder satisfaction questionnaire (OAB-SAT-q), the medical, epidemiological and social aspects of aging questionnaire (MESA), the urogenital distress inventory (UDI-6) and the female sexual function index (FSFI) along with the patient satisfaction global ratings: patient satisfaction question (PSQ), estimated percent improvement (EPI) and global perception of improvement (GPI). The SF 12 is a general quality of life questionnaire initially used to survey health status [26]. The OAB-SAT-q is a questionnaire evaluating satisfaction pertaining to overactive bladder symptom treatment, symptoms which are similar to those of a UTI [27]. The MESA questionnaire explores lower urinary tract symptoms [28]. The UDI-6 is the short form of the urogenital distress inventory which surveys life impact and symptom distress of urinary incontinence and related issues in women [29]. The FSFI is a validated questionnaire assessing female sexual function [30]. The PSQ, EPI and GPI are patient global ratings, satisfaction, perception of improvement and estimated percent improvement validated previously in the treatment of urinary incontinence [31]. These questionnaires will allow us to assess whether general quality of life, irritative urinary symptoms, as well as sexual function are improved by vaginal estrogen, which could occur secondary to the correction of atrophic vaginitis alone. We will also assess whether QOL changes when UTIs occur with less frequency and will assess overall patient satisfaction with treatment. We will also be evaluating adherence in each treatment arm. Adherence with creams will be assessed by medication diary and weighing the tubes at each 3 month visit and vaginal rings will be accounted for by confirming that the ring is still in place in the vagina and then exchanging it for the new ring. Adherence is defined as  $\geq 80\%$  usage.

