**Methodology**  
*Details of the Intervention*

Women will be randomized to one of the two vaginal estrogen arms or placebo in a 1:1:2 fashion. For those randomized to the ring, the ring will be placed by the provider in 3 month intervals at their visits. Subjects randomized to cream arm will receive 0.5g (0.312 mg) conjugated estrogen vaginal cream per vagina at bedtime two times per week. The placebo cream will be administered in a similar fashion. These cream tubes will be weighed at baseline and again at the every 3 month office visits to assess adherence. They will also be given diaries to keep track of their medication administration. Subjects will be called once a month for the first 3 months by study personnel to assess for adverse events as well as UTI symptoms. After the first 3 months, a relationship will be established with study personnel and the participants will be encouraged to call with symptoms.

Written quality of life questionnaires will be administered at baseline, at the end of randomization or 6 months and at drop out (if possible) or 12 months. The questionnaires include the OAB-SAT-q, MESA, UDI-6, FSFI and PSQ, GPI and EPI rating scales and are previously validated questionnaires referenced above in *Overall Design* [26-31]. These will assess global QOL, as well as irritative bladder symptoms and sexual function. We will also collect baseline data with respect to medical history and concomitant pelvic medicine diagnoses.

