#### *Data Analysis*

Subject characteristics including baseline measures will be compared across the randomized groups using t-test or chi-squared test (or their nonparametric / small sample counterparts) as appropriate, and will be adjusted in a regression model in addition to the primary comparisons above. It is known that even if the characteristics are balanced across the groups, such adjust can improve the efficiency of the comparisons [32]. For the secondary outcomes, frequencies (counts) of UTIs in the randomized period as well as the additional follow-up period will be compared between groups using a Poisson model; the QOL outcomes will be compared between groups using t-tests, and between baseline and 12 months within an active treatment group using paired t-test; adherence will be compared between the ring group and the active cream group as a dichotomous variable, with adherence for the latter group defined as  $\geq 80\%$ . While the primary comparisons are intent-to-treat, secondary comparisons will be carried out among those subjects who have adhered. In addition, for the variables that are collected at three or more time points, longitudinal data analysis will be performed using random effects models. As the attrition rate is expected to be as high as 20%, whether the missing data mechanism might be informative will be checking using methods such as those described by Ridout et al. [33] in case of informative (non-ignorable) missingness, sensitivity analysis will be carried out.

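### Hypothesis 2a is a single QOL claim, but the plan t-tests four to eight measures without a lead measure, decision rule or adjustment, so its false-positive rate is not controlled

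*Combined protocol and SAP*

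**What the plan says.** Section 6 (Specific Aims) states hypothesis 2 as one general claim: "Vaginal estrogen will result in improved QOL in postmenopausal women with history of recurrent UTI". Part 2a makes it "compared to placebo at 6 months". No instrument or score is named.

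Section 9, Overall Design, lists the measures. The first three are the SF-12, OAB-SAT-q and MESA. Then come "the urogenital distress inventory (UDI-6) and the female sexual function index (FSFI) along with the patient satisfaction global ratings", and the ratings are spelled out as "patient satisfaction question (PSQ), estimated percent improvement (EPI) and global perception of improvement (GPI"). That makes eight: five questionnaires and three global ratings. The section describes the SF-12 as a general QOL instrument, the OAB-SAT-q as a measure of treatment satisfaction, the MESA as covering lower urinary tract symptoms, the UDI-6 as covering incontinence-related distress and the FSFI as covering sexual function.

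Section 9, Methodology, gives a second list under the QOL questionnaires: "The questionnaires include the OAB-SAT-q, MESA, UDI-6, FSFI and PSQ, GPI and EPI rating scales". That is seven, without the SF-12.

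The between-group analysis in Data Analysis is one clause: "the QOL outcomes will be compared between groups using t-tests". The documents state only one significance level, two-sided 0.05, in Sample Size Consideration and for the primary outcome.

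**The concern.** The measures cover different things: general health, bladder symptoms, sexual function and satisfaction. A difference on the FSFI and a difference on the SF-12 would support different conclusions, yet the plan would let either be reported as support for 2a. It does not say which score decides the hypothesis, whether one positive result is enough, or what happens if the scales disagree. Hypothesis 2a therefore has no defined error rate, and the deciding scale could be settled after the results are known.

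Overall Design also notes that symptoms and sexual function may improve simply because atrophic vaginitis is corrected, so which domain carries the claim affects what it means.

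**Working it through.** **Inputs from the documents.** Completers per group: 20 (Sample Size Consideration). Significance level: 0.05 two-sided (same place, primary outcome only). Number of measures k: 8 (Overall Design), 7 (Methodology), or 4 (SF-12, MESA, UDI-6 and FSFI, leaving out the OAB-SAT-q and the three global ratings as satisfaction or global measures).

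**Assumptions.** The 5% level carries over to QOL. One significant scale could be read as support. The scales share a common correlation ρ, which the documents do not give, so a range is shown.

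**The plan's own figure.** The plan states no error rate for QOL. Its 20 per group does reproduce: for 63% versus 16%, the continuity-corrected two-proportion formula gives 20 per group, and exact power of Fisher's test at 20 per group is 82.3%, against the stated 80%. So 20 per group is used below.

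**Independent scales.** A false claim that estrogen improves QOL runs in one direction, so each two-sided 5% test contributes 2.5%. The chance of at least one is 1 − 0.975^k:

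- k = 8: 1 − 0.975^8 = 18.3%
- k = 7: 1 − 0.975^7 = 16.2%
- k = 4: 1 − 0.975^4 = 9.6%

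**Correlated scales.** Simulation of k equicorrelated two-sample t-tests, 20 per group, no true effect, 100,000 trials. Chance of at least one significant result favouring estrogen:

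| ρ | 8 scales | 7 scales | 4 scales |
|---|---|---|---|
| 0 (formula) | 18.3% | 16.2% | 9.6% |
| 0.5 | 12.7% | 11.7% | 7.8% |
| 0.7 | 9.6% | 9.1% | 6.6% |

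At ρ = 0.9 the figure for eight scales is 6.2%. One named scale gives 2.5%. For ρ from 0.7 to 0 the ratio is 9.6/2.5 = 3.8 to 18.3/2.5 = 7.3 with eight scales, and 6.6/2.5 = 2.6 to 9.6/2.5 = 3.8 with four.

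**Cost of adjusting instead.** Power by normal approximation is Φ(d√(n/2) − z). For an assumed difference of d = 0.9 SD and n = 20 per group, d√(n/2) = 0.9 × √10 = 2.846.

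- One scale at 0.05: Φ(2.846 − 1.960) = 81%
- Bonferroni over eight, 0.05/8 = 0.00625: Φ(2.846 − 2.734) = 54%

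Holm's first step uses the same 0.00625.

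**Not counted.** Data Analysis also repeats secondary comparisons in adherent women and fits random-effects models to variables measured at three or more times. Both would add tests.

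**The case against.** The strongest reply is that QOL is explicitly secondary in a 48-patient, investigator-initiated trial. The primary outcome is single, prespecified and has its own test and level, so a QOL result cannot rescue it. Leaving secondary outcomes unadjusted and reading them as supportive is common. This limits the priority of the point. It does not remove it, because the documents state QOL as a hypothesis and nowhere call it exploratory.

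Three stronger readings are tempting, and the documents do not support them:

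- *That the plan tests each scale at 5% and accepts any one as proof.* No level is given for QOL, and no section says that one positive scale suffices. The gap is silence on the rule.
- *That there are definitely eight tests.* Eight is the maximum. Overall Design speaks of satisfaction separately from QOL, although it and Methodology also introduce the whole set as QOL questionnaires. The family is ambiguous.
- *That the chance of a false QOL claim is about one in three.* The figure 1 − 0.95^8 = 34% counts results favouring placebo and assumes independence. Several scales overlap in content (three on bladder symptoms, three global ratings), so independence is unlikely.

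Correlation does reduce the inflation, but even at 0.9 the eight-scale figure is about 2.5 times nominal (6.2/2.5).

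**Conclusion.** The point holds as a gap in a secondary analysis. Hypothesis 2a has no lead measure, decision rule or adjustment, and the documents do not agree on which measures are given. The chance of a false result favouring estrogen is about 10% to 18% with eight scales, or about 7% to 10% with four, against 2.5% for one named scale. These figures rest on the 5% level carrying over to QOL, on one significant scale being read as support, and on correlations between 0.7 and 0. A reader might infer that the trial's main conclusion is compromised. It is not: the primary UTI comparison and its sample size are untouched.

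**What to change.** Before QOL data are compared by arm, state in Data Analysis one score at month 6 as the test of hypothesis 2a, with its significance level. The investigators should choose it and give their grounds. The SF-12 is the instrument that Overall Design calls a general QOL questionnaire, but Overall Design and Methodology must first be reconciled on whether it is administered. Report the other measures descriptively, with confidence intervals.

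Section 8 says enrollment is complete, so the amendment should record that QOL results by arm had not been seen. If they have been, label all QOL comparisons exploratory.

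The cost is a change of wording plus that statement. The downside is that the other scales can no longer confirm 2a on their own. Holm adjustment across all the scales is an alternative if each is meant to support the claim, but at 20 per group it costs substantial power: at its first step with eight scales, about 54% against 81% for the assumed 0.9 SD difference.

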
The open label portion of the study will start at month 6. All of those women using placebo cream will be allowed to choose a vaginal estrogen preparation to use for the remainder of the study (ring or cream). Those women initially randomized to vaginal estrogen will be allowed to choose which vaginal estrogen preparation they want to continue with. The rationale behind an open label portion of the study is an incentive to participate. Vaginal estrogen is available to patients via prescription, as an off label indication, but coverage for this therapy can be limited and treatment costly (up to \$300 per prescription refill). The open label portion of the study should provide incentive for women to enroll when the study drug is already available, as will modest reimbursement for study visits. We will also be able to compare the rates of UTI in those women who received placebo initially to their rate of UTI on drug.

Eligible women will be consented and block randomized using preset, opaque and sealed envelopes. These cards will either say “study drug 1, 2 or 3” and will be placed in numbered envelopes in a random order and selected by study staff and dispensed to the subject. These drugs will be stored in a locked cabinet in the Female Pelvic Medicine clinic. After the subject receives her study drug, she will receive administration instructions. If the assigned treatment is a ring, the subject will have it placed by the provider, if it is a cream, the cream will be weighed at baseline and she will be shown how to place it vaginally herself and instructed on bringing the remaining study drug to each 3 month visit for weighing.

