### ***Analysis***

#### ***Sample Size Consideration***

The primary outcome is whether there is any occurrence of symptomatic UTI at the end of the randomized

treatment period. Based on the literature [15] we assume that the rate of at least one UTI in the placebo group is 63%. With 20 subjects at the end of the randomized treatment period in each of the two treatment groups, we will have 80% power to detect a difference using Fisher's exact test if the corresponding rate in an active treatment group is 16% [15] under a two-sided significance level of 0.05. A total sample size of 48 (24 subjects per group) will be needed allowing for 20% attrition seen to date in the study.

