#### *Inclusion Criteria*

1. Postmenopausal status as defined by amenorrhea for  $\geq 12$  months, OR history of bilateral salpingoophorectomy, OR if the patient has had a hysterectomy defined by menopausal symptoms for  $>1$  year OR age  $>55$
2. Recurrent UTIs (3 or more in the last year or 2 or more in the last 6 months). Patients must have one culture documented UTI, but the others may be documented by urinalysis.
3. Ability to provide informed consent

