#### *Exclusion Criteria*

1. Use of any investigational drug or device within thirty days of screening
2. Urologic surgery within the past 3 months of screening or plan for surgery within one year of screening
3. Diagnosis of Interstitial Cystitis/painful bladder syndrome
4. History of urinary tract infections which require the use of IV antibiotics or where only one oral antibiotic is available for treatment, or where the risk of treatment with vaginal estrogen only is deemed unacceptable by the principle investigator secondary to the severity of prior urinary tract infections
5. Known etiology of infection such as, but not limited to: kidney or bladder stones, enterovaginal/vesical fistula, fecal incontinence, intermittent catheterization, indwelling catheter, poorly controlled diabetes
6. Urothelial cancer
7. Actively treated estrogen sensitive tumor (breast or endometrial cancer)

8. Undiagnosed vaginal bleeding
9. Inability to use a vaginal ring (secondary to advanced prolapse or shortened vaginal length)
10. Any medical reason the investigator deems incompatible with treatment with vaginal estrogen
11. Prolapse requiring pessary use

*Deferral Criteria*

1. Undiagnosed hematuria – may enroll after malignancy is ruled out
2. Use of a progestin containing intrauterine device or use of any vaginal androgens, estrogens or progestins within 3 months of enrollment – may enroll after wash out
3. Use of drugs/supplements known to prevent UTIs (ie cranberry products, prophylactic antibiotics, methenamine hippurate) 1 month prior to enrollment – may enroll after wash out if still meets inclusion criteria.

History of estrogen sensitive tumor (breast or endometrial cancer) – requires approval by the subject's primary oncologist or primary care physician

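### The month-12 quality-of-life hypothesis (2b) credits estrogen with a change from baseline, but its paired t-test has no comparator and cannot attribute the change to estrogen

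*Combined protocol and SAP*

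**What the plan says.** Secondary hypothesis 2 in section 6 is worded causally: "Vaginal estrogen will result in improved QOL in postmenopausal women with history of recurrent UTI". Part (a) compares with placebo at 6 months. Part (b) is "compared to baseline at 12 months". Data Analysis assigns between-group t-tests to the QOL outcomes and, for part (b), a comparison "between baseline and 12 months within an active treatment group using paired t-test". It then adds that "for the variables that are collected at three or more time points, longitudinal data analysis will be performed using random effects models", without naming model terms or a contrast.

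Three design features bear on part (b):

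- **Entry.** Inclusion Criteria require "Recurrent UTIs (3 or more in the last year or 2 or more in the last 6 months"). Only one of these infections needs a culture; urinalysis is enough for the rest. Under the deferral criteria, a woman using a UTI-preventive product "may enroll after wash out if still meets inclusion criteria".
- **Month 6 onward.** Overall Design states: "All of those women using placebo cream will be allowed to choose a vaginal estrogen preparation". Section 5 says that every woman receives estrogen after 6 months.
- **QOL timing.** Methodology schedules questionnaires at baseline, at 6 months, and at 12 months or drop-out.

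The documents do not call 2b descriptive, and they do not mention regression to the mean or natural course.

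**The concern.** A paired t-test asks whether the mean change differs from zero. It does not ask why. Here at least three explanations other than estrogen push in the same direction: women chosen for a high recent UTI count tend to have fewer afterwards, the condition may ease on its own, and from month 6 everyone knows she is on active drug. With no group planned to be off estrogen at month 12, the test cannot tell these apart from a drug effect.

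At stake is a secondary claim of benefit at 12 months. In a trial of this size the randomised QOL comparison (2a) could easily be null while the paired test is positive. The wording of hypothesis 2 would then let the second result be reported as an effect of estrogen. The primary UTI analysis is not affected.

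**Working it through.** **1. The plan's own figures.** No sample size, SD or effect size is given for QOL. The only calculation is for the primary outcome: "we assume that the rate of at least one UTI in the placebo group is 63"%, against 16% on active treatment, two-sided 0.05, 80% power, Fisher's exact test, 20 per group at the end of the randomised period. The continuity-corrected two-proportion formula gives 20 per group, and exact Fisher power at 20 versus 20 is 82.3%. The stated number reproduces; it is used here only as a source for n. With 1:1:2 allocation, 20 evaluable women on estrogen are 10 ring and 10 cream. The phrase in Data Analysis could mean either 10 or 20 women, and fewer may remain at month 12.

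**2. Does the entry rule produce a later fall?** Assume that each woman has a constant UTI rate, that rates follow a gamma distribution, that counts are Poisson, that nobody is treated, and that UTIs are counted in the same way before and after entry. Admit women with at least 2 UTIs in the last 6 months or at least 3 in the last 12. Population means of 0.3, 0.5 and 1.0 per 6 months were crossed with shapes of 0.5, 1, 2 and 4. Four of the 12 scenarios:

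| Mean per 6 months | Shape | Eligible women: prior 6 months | Each later 6 months | P(at least one UTI, next 6 months) |
|---|---|---|---|---|
| 0.3 | 0.5 | 1.99 | 1.10 | 0.60 |
| 0.5 | 1 | 2.00 | 1.15 | 0.62 |
| 0.3 | 4 | 1.79 | 0.44 | 0.35 |
| 1.0 | 0.5 | 2.92 | 2.47 | 0.81 |

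The later rate is lower in all 12. The first two rows lie closest to the plan's 63%. These means and shapes are assumptions.

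**3. What drift does to the paired test.** Let d be the natural mean improvement divided by the SD of the change score, with zero estrogen effect. The statistic is noncentral t with n − 1 degrees of freedom and noncentrality d√n. The chance of a significant improvement is the probability that it exceeds the 97.5% point of central t.

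- n = 10, d = 0.3: noncentrality 0.3 × √10 = 0.95, critical value 2.262, probability 13.4%.
- n = 20, d = 0.3: noncentrality 0.3 × √20 = 1.34, critical value 2.093, probability 24.6%.

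| d (assumed) | n = 10 | n = 20 |
|---|---|---|
| 0 | 2.5% | 2.5% |
| 0.2 | 8% | 13% |
| 0.3 | 13% | 25% |
| 0.5 | 29% | 56% |
| 0.8 | 62% | 92% |

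**4. The randomised comparison under the same drift.** In 20,000 simulated trials with 20 per arm and no estrogen effect, a between-arm t-test on change was significant (two-sided) in 5.0%, 5.2% and 4.9% for d = 0.3, 0.5 and 0.8. Drift common to both arms cancels.

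**The case against.** The strongest reply is that 2b openly names baseline as its comparator, that 2a already asks the causal question, and that nothing in the plan lets 2b override 2a. This is fair, and it limits the consequence. It does not remove the causal wording that governs both parts, or supply the missing control.

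Second, the chain from UTI count to QOL is not quantified. Overall Design says that no validated UTI-specific questionnaire exists. The chosen instruments cover general health, bladder symptoms, satisfaction and sexual function, and some gains are expected from treating atrophy alone. So d is unknown, may differ between instruments, and could be small for some. This stands in full: the second table in the working is a power table for assumed drifts, not an estimate of bias.

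Third, the random effects models might seem to rescue 2b. As written they have no stated contrast, and after month 6 no arm remains off estrogen.

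A reader might also infer more than the documents support:

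- *Baseline is taken when disease is at its worst.* The entry rule admits 3 infections spread over a year, no active infection is required at baseline, and wash-out can delay entry. A high recent count is documented; a peak is not.
- *The plan's own 63% proves spontaneous improvement.* P(no UTI) = 1 − 0.63 = 0.37 gives a Poisson mean of −ln 0.37 = 0.99 per 6 months, below the entry floor of 2, or 3/2 = 1.5. With gamma heterogeneity of shape k among enrolled women, the mean is k(0.37^(−1/k) − 1): 1.70 at k = 1 and 3.15 at k = 0.5. The comparison can therefore vanish or reverse. It also sets entry infections that urinalysis may document against outcome infections that need a culture.
- *The test uses 40 women.* Overall Design pools placebo starters' results after 6 months on estrogen with the active arms' 6-month results. That is not the change from baseline to month 12 in Data Analysis.

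**Conclusion.** The concern holds. Hypothesis 2b makes a causal claim that its named test cannot support, because the test has no comparator, entry selects on a high recent UTI count, and no off-estrogen group is planned after month 6.

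The direction of the bias is supported, on the premise that QOL improves as UTIs become fewer, a link that Overall Design itself sets out to examine. Open-label expectation would add to it. The size is unknown. At an assumed drift of 0.3 SD the false-positive chance is about 13% with 10 women and 25% with 20, instead of 2.5%. The range for drifts of 0.2 to 0.8 SD is 8% to 62% and 13% to 92%.

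It would be too strong to say that the paired test will usually be positive without a drug effect. That depends on a drift the documents do not give. It would also be too strong to say that QOL efficacy goes untested: 2a is a randomised comparison and is free of this bias.

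**What to change.** 1. State that the QOL efficacy claim rests on the randomised comparison with placebo at 6 months (2a).
2. Reword 2b as a descriptive change from baseline to month 12, with a confidence interval and no causal claim. Say which women it covers: ring, cream or both.
3. Report the placebo arm's change from baseline to month 6 beside it, as a benchmark for natural course. The benchmark is imperfect. It covers 6 months rather than 12, does not include open-label expectation, and takes early assessments from women who reach 3 UTIs.
4. If a longitudinal contrast is wanted, the arm-by-visit comparison of the month 6 to 12 change may be shown as supportive only. With P for placebo starters and E for estrogen starters, (P12 − P6) − (E12 − E6) = (P12 − E12) − (P6 − E6). If the arms converge on estrogen by month 12, this is the month-6 difference with its sign reversed plus month-12 noise. It leaves open-label expectation uncontrolled, and it is disturbed by the free choice of preparation at month 6 and by early crossover after 3 UTIs. It is not a controlled month-12 efficacy result.

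The cost is wording in section 6 and Data Analysis plus one extra table row; all the data are already scheduled. The downside is that 2b loses its within-group p-value as evidence of efficacy.

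### Intent-to-treat is stated only for the primary comparison; as worded, the plan would let the randomised secondary comparisons of UTI rate (1a) and 6-month QOL (2a) be run among adherent women

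*Combined protocol and SAP*

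**What the plan says.** The Data Analysis section first lists the secondary analyses. For UTI counts, "frequencies (counts) of UTIs in the randomized period as well as the additional follow-up period will be compared between groups using a Poisson model". For quality of life, "the QOL outcomes will be compared between groups using t-tests". For adherence, "adherence will be compared between the ring group and the active cream group as a dichotomous variable". None of these clauses names a population. The only population rule follows: "While the primary comparisons are intent-to-treat, secondary comparisons will be carried out among those subjects who have adhered".

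Section 6 (Specific Aims) states the hypotheses. Hypothesis 1a is that "Overall rates of UTI in the first 6 month period in those women receiving vaginal estrogen will be" lower than on placebo. Hypothesis 2a is that QOL improves "compared to placebo at 6 months". Neither is limited to adherent women. Hypothesis 4 is: at 6 and 12 months, "vaginal estrogen will be effective at preventing UTI in those adherent to therapy".

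Adherence is assessed at the 3-month visits. The Overall Design and Outcomes sections set at least 80% use for creams, judged by tube weight with a diary. For the other product, "vaginal rings will be accounted for by confirming that the ring is still in place in the vagina". Allocation is 1:1:2 to ring, active cream and placebo cream (Details of the Intervention).

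**The concern.** The rule sets primary against secondary and contains no word such as additional or supportive. An analyst who follows it literally would test 1a and 2a in adherent women. Adherence arises after randomisation and can be changed by a UTI, by discomfort or by lack of benefit, so the groups compared would no longer be the randomised groups.

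The filter is also uneven between the arms. Every placebo woman must pass the cream test, but only about half of the estrogen women must; the rest need only have the ring in place at the visit. If cream users who become infected tend to stop, infected women leave the placebo group more readily than the estrogen group.

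Even on a milder reading, the population for 1a and 2a is unstated and could be chosen after the results are seen.

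**Working it through.** **1. Which secondary hypotheses the sentence can govern**

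- 1a and 2a: randomised comparisons with placebo, with no adherence limit in the hypothesis and no population in the analysis clause. The literal rule reaches both.
- 1b and 2b: change within women over time. They have no protection from randomisation to lose.
- 3: ring against cream on adherence itself. Among adherers both groups are 100% adherent, so the rule cannot apply.
- 4: expressly about adherent women. The sentence is the only one in the section that supplies its analysis.

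**2. The plan's own figure**

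The plan states 80% power with 20 per group, 63% against 16%, Fisher's exact test, two-sided 0.05. Exact enumeration gives 78.4% at 18 per group, 81.6% at 19 and 82.3% at 20. The figure is sound and belongs to the primary comparison. The present point does not alter it.

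**3. Illustration A: cream users tend to stop after infections**

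From the plan: 63%, 16%, 20 per group, and an estrogen group half ring, half cream. Assumed, because the documents give no adherence rates: Poisson counts; cream users adherent with probability 0.9, 0.7 or 0.5 after 0, 1, or 2 or more UTIs; ring users 0.95 throughout.

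- Mean UTIs on placebo: −ln(1 − 0.63) = 0.994. At the plan's active rate: −ln(1 − 0.16) = 0.174.
- At mean 0.994, the probabilities of 0, 1, and 2 or more UTIs are 0.370, 0.368 and 0.262.
- Adherent share of cream users: 0.9 × 0.370 + 0.7 × 0.368 + 0.5 × 0.262 = 0.722.
- UTIs among them, per woman randomised: 0.7 × 0.368 + 0.5 × (0.994 − 0.368) = 0.571.
- Placebo mean among adherers: 0.571 / 0.722 = 0.79.
- Estrogen mean among adherers with no drug effect: (9.5 × 0.994 + 7.22 × 0.791) / (9.5 + 7.22) = 0.91.

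The same steps with other true effects give:

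| True rate ratio | Estrogen mean, adherers | Rate ratio, adherers | Women left of 40 |
|---|---|---|---|
| 1.00 | 0.91 | 1.15 | 14.4 + 16.7 = 31.1 |
| 0.50 | 0.446 | 0.56 | 14.4 + 17.5 = 31.9 |
| 0.175 (plan: 0.174 / 0.994) | 0.155 | 0.196 | 14.4 + 18.2 = 32.6 |

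**4. Illustration B: other patterns, no drug effect**

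If a share a of a group adheres and its non-adherers have k times the adherers' rate, the adherers' mean is 0.994 / (a + (1 − a)k). Type I error comes from 20,000 simulated trials per row, 20 per group, with a Poisson rate test at two-sided 0.05. All a and k are assumed.

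| a, placebo / estrogen | k, placebo / estrogen | Rate ratio, adherers | Type I error, adherers | Type I error, all randomised |
|---|---|---|---|---|
| 0.8 / 0.8 | 1 / 1 | 1.00 | 4.9% | 4.9% |
| 0.8 / 0.8 | 2 / 2 | 1.00 | 5.2% | 6.4% |
| 0.9 / 0.7 | 2 / 2 | 0.85 | 6.7% | 6.1% |
| 0.9 / 0.6 | 2 / 2 | 0.79 | 7.9% | 6.3% |
| 0.8 / 0.8 | 1 / 3 | 0.71 | 13.6% | 7.1% |
| 0.9 / 0.7 | 1 / 3 | 0.625 | 20.0% | 6.9% |
| 0.9 / 0.6 | 1 / 3 | 0.56 | 24.0% | 6.6% |

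Example, last row: 0.994 / (0.6 + 0.4 × 3) = 0.552, and 0.552 / 0.994 = 0.56. The all-randomised column exceeds 5% where rates differ between women, which a simple Poisson test ignores.

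**The case against.** The strongest reply is that the sentence merely adds an analysis. The secondary outcomes have already been listed as between-group comparisons without restriction. Hypothesis 4 requires an analysis in adherent women, and without this sentence it would have none. Hypothesis 3 cannot be tested among adherers, so the sentence cannot literally cover every secondary outcome. And if all secondary outcomes were confined to adherers, a separate hypothesis 4 would be largely redundant for UTI.

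This argument stands, and it rules out the stronger inference that the plan has decided to analyse 1a and 2a only in adherent women and has thereby given up randomisation for them. It does not supply the missing statement: even on the additive reading, no section says in whom 1a and 2a are analysed.

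It is also fair to say that the bias may be small. With the plan's own effect, Illustration A moves the ratio only from 0.175 to 0.196. Where adherence is equal in both arms and related to risk in the same way, Illustration B shows no inflation from the selection. The marked inflation needs estrogen-arm non-adherers alone to have three times the rate.

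**Conclusion.** The point holds as an ambiguity with a harmful literal reading. Intent-to-treat is given only to the primary comparison, 1a and 2a have no stated population, and the one available rule would, as worded, place them in a subset formed after randomisation by criteria that differ between cream and ring.

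How far this would move the 1a result is unknown. With no drug effect, the assumed patterns give ratios among adherers from 1.15, against estrogen, down to 0.56, in its favour. These figures illustrate possible bias and do not estimate it; a reader should not infer that the bias favours either side. Nothing here quantifies 2a, since the documents give no basis for linking QOL scores to adherence.

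The primary conclusion, sample size and power are untouched. The change should be made, but the matter does not threaten the trial's main result.

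**What to change.** Replace the sentence in Data Analysis with:

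> Hypotheses 1a and 2a are analysed in all randomised women in their randomised group (intent-to-treat). Analyses among adherent women address hypothesis 4 only and are supportive and non-randomised. Hypothesis 3 is assessed in all women assigned to ring or active cream.

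The cost is one replaced passage of text: no new data, and no change to sample size, significance level or treatment. Enrolment is complete according to the Progress Report, so the revision should be dated and made before the secondary outcomes are compared by group.
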